Most of the acute (peri)pancreatic fluid collections (PFC) resolve spontaneously with conservative management [5]. However, about 25% of patients with acute necrotic collections (ANC) and nearly 50% of those with walled-off necrosis (WON) eventually require intervention [6,7].

The management of PFC and WON had a paradigm shift over the last three decades. Open necrosectomy was considered standard of care [8] until 1991 when Bradley and Allen demonstrated that conservative management is associated with better outcomes compared to surgical intervention in patients with acute sterile necrotising pancreatitis in the absence of infection [9]. Historically, open surgical necrosectomy was the standard approach for managing infected necrotising pancreatitis and symptomatic sterile peripancreatic fluid collections (PFCs). However, this approach is associated with substantial perioperative stress, collateral tissue injury, and long-term complications, including pancreatico-cutaneous fistulas, exocrine and endocrine insufficiency, and incisional hernias [10-12].

Subsequently, the step-up approach beginning with percutaneous drainage followed by video-assisted retroperitoneal debridement when necessary—emerged as the preferred management strategy, as established by the landmark PANTER trial [13].

Simultaneously there was emergence of endoscopic particularly endoscopic ultrasound (EUS) guided procedures. Multiple series from centres across Europe and the United States have

validated the efficacy of endoscopic transluminal necrosectomy [14,15]. Furthermore, a pilot multicentre randomized controlled trial involving 22 patients suggested that endoscopic transluminal necrosectomy may offer advantages over surgical necrosectomy, particularly with respect to reducing the risk of new-onset multiple organ failure and overall complication rates[16].

Subsequently, EUS-guided drainage and necrosectomy have been widely adopted as the standard and first line treatment for WON in most patients [17].

Nutritional support is important in management of severe acute and necrotizing pancreatitis. Multiple randomized controlled trials and meta-analyses have demonstrated that enteral nutrition is superior to parenteral nutrition in reducing infections, surgical intervention rates, and mortality in patients with acute pancreatitis[18,19].These infections are thought to be mediated by bacterial translocation from the gut due to disturbed bacterial overgrowth and increased mucosal permeability. However, the timings to initiate enteral feeding is not clear. Nonrandomized studies in acute pancreatitis have shown that initiating naso-enteric tube feeding within 48 hours of admission, as opposed to later initiation, is associated with a significant reduction in major infectious complications and, in some studies, a decrease in mortality [20-22].Based on these studies the European guidelines recommend early initiation of enteral feeding within 24-72 hours[23].

However, there are no studies to guide the feeding strategies in patients with pancreatic fluid collections undergoing endoscopic transluminal drainage with LAMS and Endoscopic necrosectomy.

Hence, we have designed an RCT to suggest feeding strategies in patients undergoing EUS-guided cystogastrostomy (EUS-CG) in WON.

Review of Literature

Gut dysfunction in Acute pancreatitis (AP)

The gastrointestinal tract has traditionally been viewed as an innocent bystander in critical illness, sustaining collateral damage. Reflex splanchnic vasoconstriction, aimed at preserving perfusion of vital organs, leads to ischemic injury, while subsequent resuscitation may exacerbate damage through reperfusion injury[24].One of the key pathological events following intestinal injury is the disruption of the epithelial barrier, leading to increased permeability. This breakdown permits the translocation of luminal bacteria and endotoxins into the portal venous system and mesenteric lymphatics, potentially triggering systemic inflammatory responses[25]. Gut barrier dysfunction in acute pancreatitis facilitates bacterial

translocation from the intestinal lumen into the systemic circulation, thereby playing a critical role in the development of secondary infections. This microbial translocation contributes to systemic inflammatory responses, increasing the risk of sepsis, multiorgan failure, and ultimately, mortality[26]. Studies have shown that the microorganisms implicated in sepsis and pancreatic infections in acute pancreatitis are predominantly of enteric origin [24,27]. On index endoscopy, the most commonly identified organisms were Enterococci (45%), followed by Enterobacteriaceae (42%) and fungi (22%) [28,29].

Nutrition in acute pancreatitis (AP)

Nutritional management in AP is an important aspect in treatment of AP.

1. Malnutrition in AP and its impact on outcome

Patients with acute pancreatitis are in hypercatabolic state and are at nutritionally high risk especially those with moderately severe or severe disease. The persistent acute inflammatory response leads to enhanced protein catabolism, third-space fluid shifts, and increased oxygen extraction from the bloodstream, thereby compromising the perfusion of vital organs. Additionally, impaired gut barrier function or infected pancreatic necrosis—resulting from enzymatic leakage—may further progress to sepsis[23]. One study showed that malnutrition in acute pancreatitis is associated with higher rates of death, sepsis, severe sepsis, septic shock, and respiratory failure [46]. Moreover, poor nutritional status is linked to adverse post-discharge outcomes, including increased dependence in activities of daily living, greater likelihood of requiring nursing home care, and higher mortality within one year following hospital discharge [47].

2. Enteral feed versus TPN:

Enteral nutrition helps maintain gut mucosal integrity, promotes intestinal motility, prevents bacterial overgrowth, and enhances splanchnic blood flow [30]. Multiple randomized controlled trials, systematic reviews, and meta-analyses have consistently shown that enteral nutrition is safe and well-tolerated in patients with severe acute pancreatitis, leading to significant improvements in clinical outcomes such as reduced infectious and gastrointestinal complications, lower risk of tracheal aspiration, less pain exacerbation, earlier achievement of energy balance, decreased need for surgery, shorter hospital stays, reduced incidence of multi-organ failure, and lower mortality [31]. A recent meta-analysis by Wu et al., including 11 randomized controlled trials

and 562 patients with severe acute pancreatitis, compared the efficacy of enteral nutrition (EN) versus parenteral nutrition (PN). The study demonstrated that EN significantly reduced the relative risk of mortality ($RR = 0.43; P = 0.006$), infections and complications ($RR = 0.53; P < 0.001$), and was associated with a lower need for surgical intervention and a shorter duration of hospitalization compared to PN. No significant difference in the incidence of multiple organ failure (MOF) was observed between the EN and PN groups ($RR = 0.63; P = 0.059$) [32]. Enteral nutrition may prevent infection of pancreatic necrosis in patients with severe acute pancreatitis [33,34]. A Cochrane meta-analysis of eight randomized controlled trials concluded that, compared to parenteral nutrition, enteral nutrition significantly reduced mortality, systemic infections, and the incidence of multiorgan failure in patients with acute pancreatitis [19]. However, several randomized trials have linked total parenteral nutrition (TPN) with an increased risk of infections and other complications. Therefore, PN should be used cautiously and only when enteral nutrition is not feasible, not tolerated, or insufficient to meet caloric needs [35].

3. Limitations of oral feeding in ANP and WON patients:

Oral feeding intolerance (OFI) is a well-recognized clinical complication in the management of acute pancreatitis (AP). It is defined by the recurrence of gastrointestinal symptoms—including abdominal pain, nausea, and vomiting on reintroduction of oral nutrition. OFI is frequently associated with biochemical derangements and increased analgesic requirements during hospitalization. Several previous studies have demonstrated that patients with oral feeding intolerance (OFI) experience a significantly prolonged length of hospitalization (LOH), with hospital stays averaging 5 to 35 days longer compared to those without OFI [36]. An international prospective cohort study conducted to evaluate the incidence, clinical predictors, and outcomes of oral feeding intolerance (OFI) in patients with acute pancreatitis (AP) reported that OFI developed in 13% of the study population [37]. Bevan et al. reported an overall incidence of OFI at 16% in a meta-analysis including centres from multiple continents [36].

The same meta-analysis identified the risk factors for OFI which includes peripancreatic fluid collection (PFC). The patient with peripancreatic fluid collection are at risk of OFI 3.5 times more than those without them. These symptoms may be attributed to the mass effect of the fluid collection, which can exert compressive pressure on the stomach, duodenum, and

jejunum, leading to early satiety, vomiting, abdominal pain, and bloating. Other risk factors are pleural effusion and higher Balthazar and Ransom score [36].

4. How to improve enteral nutrition role of NJ feeds

Three randomized controlled trials comparing nasojejunal and nasogastric feeding routes in patients with severe acute pancreatitis found no significant differences in terms of feeding tolerance, complication rates, or mortality [38-40]. Four meta-analyses [41-44] have concluded that nasogastric tube feeding is a feasible, safe, and well-tolerated approach in patients with severe acute pancreatitis. Compared to nasojejunal feeding, it does not lead to higher rates of complications, mortality, recurrence of refeeding pain, or extended hospital stay. Unfortunately, to date, there have been no published studies specifically addressing the topic of nutritional support in patients with pancreatic collections treated using minimally invasive approaches. In a large Dutch trial demonstrating the superiority of the endoscopic approach over the surgical step-up strategy [84], specific data on nutritional support were not reported. However, all patients were provided with oral nutrition when tolerated. In cases of oral intolerance, enteral nutrition was delivered via a nasojejunal feeding tube, and parenteral nutrition was administered when enteral nutrition was contraindicated [45].

Aims and Objectives:

Aim:

To compare outcomes of Nasojejunal feeding vs oral feeding following endoscopic transluminal drainage in patients with symptomatic walled-off necrosis

Primary Objectives:

1. To compare the rate of nutritional failure at Day 14 between Nasojejunal and oral feeding post endoscopic transmural drainage of WON.

Secondary Objectives:

1. To compare infection rates, need for antibiotic escalation and new onset organ failure
2. To compare re-intervention needs and hospital stay duration
3. To compare patient weight, serum albumin and inflammatory markers (CRP)
4. To compare GI complications (Vomiting, diarrhoea, aspiration pneumonia, feeding intolerance)
5. To compare patient reported outcomes (appetite, pain ,quality of life)

Materials and Methods:

Study design

The study will be a prospective, open label, single centre, randomized controlled trial. It will be conducted in the Department of Gastroenterology, PGIMER, from July 2025 to December 2026

Study Population:

All patients presented to PGIMER with WON due to acute pancreatitis requiring EUS guided transluminal drainage will be screened for inclusion criteria.

Inclusion criteria

1. Patients of acute pancreatitis (AP) with 18-75 years of age
2. Patients with symptomatic WON requiring EUS guided transluminal drainage
3. Provision of written informed consent

Exclusion criteria

1. Patients with collection not amenable for EUS guided drainage (distance of WON >1 cm from the gastrointestinal lumen)
2. Known malignancy or immunocompromised state
3. Previous upper gastrointestinal(GI) surgery interfering with absorption
4. Active GI bleeding
5. GI obstruction, ileus or persistent vomiting
6. Patients moribund to undergo endoscopic procedure (Glasgow coma scale <8 or patients on ventilatory support)
7. Patients with irreversible coagulopathy like platelets <50,000/mm³ and/or INR>1.5
8. Pregnant or lactating female

WON: WON will be defined as a mature, encapsulated collection of pancreatic and/or peripancreatic necrosis that has developed a well-defined inflammatory wall. [3]

Symptomatic WON: It will be defined by any of the following: 1) Infected WON, or 2) Presence of pressure symptoms like abdominal pain, early satiety, weight loss or biliary duct compression or 3) persistent pain abdomen

Infected WON: It will be defined by any of the following: 1) As evident on by a positive Gram's stain or culture from a fine-needle aspiration or 2) the presence of gas configurations within collection on contrast-enhanced computed tomography (CT) or 3) clinical signs of infection; defined as persistent organ failure or persistence of two inflammatory variables (temperature $>38.5^{\circ}\text{C}$ or elevated C-reactive protein levels or leukocyte counts) during 3 consecutive days.

SIRS: Presence of ≥ 2 out of the following parameters: Temperature $< 36^{\circ}\text{C}$ or $>38^{\circ}\text{C}$, Total leukocyte count $< 4000/\text{mm}^3$ or $>12000/\text{mm}^3$, Respiratory rate $> 20/\text{min}$ or PaCO_2 of $< 32\text{mmHg}$, Heart rate $> 90/\text{minute}$ [41]

Organ failure- It will be defined as per modified Marshall criteria [4]

Technical success: Successful placement of metal stent with EUS guided transluminal drainage.

Clinical success: Post endoscopic treatment collection size ≤ 3 cm on any cross-sectional imaging before removal of metal stent along with resolution of initial symptoms requiring drainage.

Randomization: Patients needing EUS guided drainage with LAMS for symptomatic WON will be randomized once they fulfil inclusion criteria. Computer generated randomization assignments will be provided in advance using block randomisation and placed in sequentially numbered sealed envelopes. They will be opened during the procedure to determine treatment allocation.

Study flow:

Patients of AP with infected WON who are planned for EUS guided transluminal drainage by LAMS will be screened for inclusion criteria. Patients who fulfilled inclusion criteria will be randomized into either Nasojejunal (NJ) feeding or oral feeding after informed consent.

[figure not shown]
Sample size:

Since it is a pilot study and in a year the unit treats approximately 80-100 patients with WON and therefore considering exclusions a feasibility sample size of 20 in each arm will be taken.

Techniques:

Initial diagnostic EUS:

EUS examination will be done under conscious sedation using intravenous midazolam. Linear scanning echoendoscope (EG-3870 UTK linear echoendoscope, Pentax Inc., Tokyo, Japan or

UCT180 linear echoendoscope, Olympus Optical Co Ltd, Tokyo, Japan) will be used at a frequency of 7.5 MHz. The WON and surrounding areas will be first carefully scanned on EUS with special emphasis on size as well as detailed morphology of WON. Colour Doppler will be used to detect any intervening vascular collaterals.

Quantification of solid necrotic debris on EUS:

The echogenic material present in the WON is suggestive of solid necrotic debris. An attempt to quantify the amount of solid debris as percentage of total size of collection will be done. The quantification of the solid debris will be an approximate visual judgment of the endoscopist.

Randomization:**A. Nasojejunal (NJ) feeding group:**

- Patients randomized to this group will have NJ placement within 24 hours post-drainage.
- NJ will be placed endoscopically
- NJ position will be confirmed by Abdominal X-ray (AXR)
- Standard formula feed will be initiated immediately after placing and confirming the NJ position with a rate of
 - First 24 hours : 25 ml/hr
 - Between 24-48 hours : 50 ml/hr
 - Between 48-72 hours: increase to full nutrition
 - After 72 hours: Full nutrition
- Full nutrition is defined as an energy target of 30kcal/kg/day

.

B. Oral feeding group:

- Patients randomized to this group will initiated on oral feed post procedure as tolerated.
- Patient will be started on oral liquid then on soft diet. Escalation will be guided based on feed tolerance. Oral diet will be supplemented with parenteral nutrition if caloric intake is <60% of target calorie at Day 5.

Nutritional failure at Day 14:

Definition:

- <75% calorie requirements are met
- Need for parenteral nutrition
- Severe GI intolerance requiring feed modification

Infectious complications:

The patient should have signs of bacterial infections/fungal infections i.e. body temperature $>100^0$ F and raised leukocytes, CRP, Procalcitonin, beta-D glucan and galactomannan.

| Infection | Definition |
|-------------------------------------|---|
| Infected pancreatic necrosis | Positive culture after first percutaneous drainage procedure of collection with (peri-) pancreatic necrosis |
| Bacteremia | Positive blood culture Positive culture in 1 blood culture. In case of coagulase negative staphylococci or other non-virulent micro-organisms at least 2 blood culture bottles are mandatory. |
| Pneumonia | Coughing, dyspnoea, radiography with infiltrative abnormalities and positive culture in sputum. On the intensive care unit, a positive endotracheal culture is mandatory |
| Sepsis | SIRS and positive blood culture |
| | |

Statistical analysis:

All patients after randomization will be evaluated for primary and secondary endpoints. Data will be explored for any outliers, errors and missing values. When data will be normally distributed, continuous variables will be compared using Student's t-test. For skewed data, Mann-whitney test will be used. Quantitative data will be described as median with range and mean with standard deviation. Categorical data will be shown as proportions. Multiple linear regression analysis will be performed to identify risk factors for requirement of additional intervention after initial drainage procedure. 95% confidence interval will be taken as a cut-off for significance. Intention to treat and per-protocol analysis will be performed. The analysis was performed using Statistical Packages for the Social Sciences (SPSS Inc, Chicago, IL, version 22.0 for windows).

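### Does opening the allocation envelope at an unnamed moment in the drainage procedure put the comparison at risk?

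*Protocol*

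**What the plan says.** The Protocol speaks of the timing of randomisation in three places.

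- **Randomization section, eligibility:** "Patients needing EUS guided drainage with LAMS for symptomatic WON will be randomized once they fulfil inclusion criteria".
- **Randomization section, envelopes:** assignments are computer generated in blocks and kept in sequentially numbered sealed envelopes. Then: "They will be opened during the procedure to determine treatment allocation".
- **Study flow:** "Patients who fulfilled inclusion criteria will be randomized into either Nasojejunal (NJ) feeding or oral feeding after informed consent".

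The related provisions are:

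- Exclusion criterion 1 removes "Patients with collection not amenable for EUS guided drainage (distance of WON >1 cm from the gastrointestinal lumen").
- The definitions include "Technical success: Successful placement of metal stent with EUS guided transluminal drainage".
- Under Techniques, "The WON and surrounding areas will be first carefully scanned on EUS with special emphasis on size as well as detailed morphology of WON". Solid debris is then estimated, and "The quantification of the solid debris will be an approximate visual judgment of the endoscopist". The heading for randomisation, with the two arms, follows.
- In the nasojejunal (NJ) arm, "Patients randomized to this group will have NJ placement within 24 hours post-drainage". The oral arm starts feeding once the procedure is over.
- The Statistical analysis section evaluates every randomised patient and plans both intention-to-treat and per-protocol analyses.

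**The concern.** The procedure is a series of steps: diagnostic scan, debris estimate, stent placement. Some of them depend on the operator. An opening time given only as some point in that series leaves room for the endoscopist to know the arm, in an open-label trial, while deciding whether the collection can be drained, estimating debris and placing the stent. The definition of technical success implies that placement can fail. A patient randomised before a failed placement would stay in the intention-to-treat comparison, although the aim is to compare feeding after drainage. Neither arm needs its allocation before drainage, so early opening would gain nothing. With 20 patients per arm, one patient is 1/20 = 5 percentage points of an arm, so even a single such case seems worth attention.

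**Working it through.** The Protocol gives no figure on this point to reproduce: no rate of failed or abandoned drainage, and no assumed event rate. The check is mainly a reading of the text, followed by an illustration of size.

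**1. Do the three timing statements conflict?** No. Eligibility and consent are conditions for randomisation. The envelope sentence says when the assignment is revealed. A patient can meet the criteria, consent, enter the procedure and have the envelope opened after the stent is placed, and all three statements are then satisfied.

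**2. Which order does the visible text suggest?** Under Techniques the order is scan, debris estimate, randomisation. In the Thesis Proforma the index drainage table (collection size, necrosis percentage, stent used, periprocedural complications) comes before the randomisation heading. Both fit late opening. The study-flow figure, which may show the step, is missing from the text available here, and its absence cannot be held against the plan.

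**3. Does eligibility depend on the scan?** Exclusion criterion 1 is a distance limit, and the Protocol does not say that it is measured at EUS. Patients are screened when drainage is already planned, and the Proforma has an imaging column for before the procedure. The distance may be settled beforehand.

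**4. Could knowing the arm bias the result?** The arms differ only in feeding after drainage. Nothing in the Protocol suggests that the intended feeding route would alter stent placement. The debris percentage is neither an objective nor part of the definition of nutritional failure. The trial is open label, so later decisions are made with the arm known whenever the envelope is opened.

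**5. Size, if a failed drainage were randomised early.** Assumed Day 14 nutritional failure rates, not from the Protocol: oral 40%, NJ 20%, true difference 20 points, n = 20 per arm. One undrained patient in one arm only:

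| Arm of the undrained patient | Outcome | Rate in that arm | Difference, oral minus NJ |
|---|---|---|---|
| NJ | failure | (19 × 0.20 + 1)/20 = 24% | 40 − 24 = 16 |
| NJ | no failure | 19 × 0.20/20 = 19% | 40 − 19 = 21 |
| Oral | failure | (19 × 0.40 + 1)/20 = 43% | 43 − 20 = 23 |
| Oral | no failure | 19 × 0.40/20 = 38% | 38 − 20 = 18 |

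The shifts go both ways. Let q be the patient's chance of nutritional failure, the same in either arm. The expected difference is 21 − 5q if the patient is in the NJ arm and 18 + 5q if in the oral arm. With either arm equally likely, the mean is (21 − 5q + 18 + 5q)/2 = 19.5 points for any q. One such patient in each arm gives 20 × (1 − 1/20) = 19 points.

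The standard error of the difference on the same rates is √(0.40 × 0.60/20 + 0.20 × 0.80/20) = √0.020 = 0.141, or about 14 points. The expected shift is 0.5 to 1 point, and the largest single-patient shift is 4 points.

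**6. How often could it happen?** With all 40 envelopes opened before drainage and an assumed failed-drainage rate f, the expected number is 40f and the chance of at least one is 1 − (1 − f)^40.

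| f (assumed) | Expected number | Chance of at least one |
|---|---|---|
| 2% | 0.8 | 55% |
| 5% | 2 | 87% |
| 10% | 4 | 99% |

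Even at 10%, the average effect is dilution by 1 − 0.10, from 20 to 18 points.

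**The case for a change.** The strongest case for the concern is that the order of headings and form fields is not a rule. The explicit timing statements tie randomisation to eligibility and consent, not to a placed stent. Even if the distance criterion is settled on earlier imaging, technical success is known only during the procedure. Numbered envelopes and intention-to-treat analysis discourage selective removal of patients, but they do not stop the operator from knowing the arm, and they do not keep undrained patients out of a comparison defined after drainage. The per-protocol analysis can set such patients aside only by exclusion after randomisation. The moment of opening is a matter of trial conduct, so it would not ordinarily be left to a statistical analysis plan.

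Much of this stands as description. No visible sentence names the step, early opening is not forbidden, and neither arm needs its allocation sooner. It does not follow that the plan is wrong. Keeping a failed drainage in the intention-to-treat set is what that analysis is meant to do. Barring such patients from randomisation would narrow the randomised population, which is a reasonable design preference rather than the repair of a fault. The argument from operator knowledge still lacks a reason why the feeding route would influence the drainage.

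**Conclusion.** The concern is not upheld. The Protocol states nothing false or contradictory here: its wording admits opening after stent placement, and the visible order of the Techniques section and the Proforma points that way. If opening did come earlier, the consequence would be a little dilution and noise. On the assumed 40% and 20% rates, the expected loss is 0.5 point for one undrained patient in either arm, 1 point for one in each arm, and 2 points if 10% of patients were undrained, against a standard error of about 14 points in a trial that the Sample size section calls a pilot with a feasibility sample size. These figures rest on assumed event and failure rates, on undrained patients having the same outcome risk in both arms, and on the success of drainage not depending on the allocated feeding route. The Protocol gives no ground to doubt the last of these. What remains is a detail that the text leaves implicit and that the missing figure may already show.

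### Parenteral nutrition has a starting rule in the oral arm only but counts as primary-endpoint failure in both arms, so equal intake can be scored differently by arm

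*Protocol*

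**What the plan says.** The primary objective (Protocol, Aims and Objectives) compares the rate of nutritional failure at Day 14 between NJ and oral feeding. Study design makes the trial open label, and Sample size sets 20 patients per arm on feasibility grounds.

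- **Oral arm** (Randomization, B. Oral feeding group): "Oral diet will be supplemented with parenteral nutrition if caloric intake is <60% of target calorie at Day 5".
- **NJ arm** (Randomization, A. Nasojejunal (NJ) feeding group): tube placement, X-ray confirmation and a stepped rate, ending with "After 72 hours: Full nutrition". The target is given as "Full nutrition is defined as an energy target of 30kcal/kg/day". The section neither sets a PN criterion nor bars PN.
- **Endpoint** (headed "Nutritional failure at Day 14"): three components, namely intake below 75% of requirement, "Need for parenteral nutrition", and "Severe GI intolerance requiring feed modification". None is limited to one arm, the need for PN is not defined, and the list is not joined by any or all.
- **Background** (Review of Literature, Enteral feed versus TPN): "PN should be used cautiously and only when enteral nutrition is not feasible, not tolerated, or insufficient to meet caloric needs". This is a literature statement without a threshold.

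The Thesis Proforma records calorie intake at Days 0, 1, 2, 5, 8, 11 and 14 in both arms, in a single row that does not separate PN calories.

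**The concern.** A treatment instruction in one arm produces an event that the primary endpoint counts as failure. In the other arm the same event depends on the judgement of clinicians who know the allocation. Part of an observed difference in failure rates could then reflect unequal PN rules rather than the feeding route.

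In a pilot of this size the main harm is a distorted failure-rate difference carried into the planning of a later trial.

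**Working it through.** The protocol gives no event rate or expected difference, so there is no figure to reproduce.

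**1. One patient under each arm's rules.** Intake is 55% of target on Day 5 and 80% on Day 14, without severe GI intolerance. Any single component is taken to be enough for failure, which is the natural reading of the list.

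| Reading of the PN component | Oral arm | NJ arm |
|---|---|---|
| PN at any time up to Day 14 | Failure, by rule | Failure only if the clinician chose PN |
| PN status on Day 14, still running | Failure | Failure only if PN was chosen and is still running |
| PN status on Day 14, stopped earlier | Success | Success |

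Patients below 75% on Day 14 fail in either arm. The different scoring therefore falls on those who are low at Day 5 and recover.

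**2. Size when intake is the same in both arms (all inputs assumed).** Let q be the share below 60% at Day 5 who reach at least 75% by Day 14 with no other failure. Let r be the share of such NJ patients given PN by choice, and b the share failing on the other criteria. Under the any-time reading:

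- oral failure rate = b + q
- NJ failure rate = b + q × r
- artificial gap = q × (1 − r)

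| q | Gap, r = 0 | Patients of 20 | Gap, r = 0.5 | Gap, r = 1 |
|---|---|---|---|---|
| 5% | 5 points | 1 | 2.5 | 0 |
| 10% | 10 | 2 | 5 | 0 |
| 20% | 20 | 4 | 10 | 0 |
| 30% | 30 | 6 | 15 | 0 |

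With b = 20% and r = 0, exact enumeration of two binomials of size 20 gives a Fisher p-value below 0.05 in 3.3%, 6.2%, 19.2% and 40.9% of trials for these four values of q. Without any gap the figure is about 2.0% to 2.5%. Fisher's test is my choice, since Statistical analysis names no test for proportions.

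**3. The sign can reverse.** NJ clinicians may also give PN to patients at or above 60%. Let d be the share of otherwise successful NJ patients in that group who get it. Assume 30% are low at Day 5, half of them recover (q = 0.30 × 0.50 = 0.15), and 7% of the others fail anyway:

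gap = 0.15 × (1 − r) − 0.70 × 0.93 × d = 0.15 × (1 − r) − 0.651 × d

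- r = 0: 15 points at d = 0, 8.5 at d = 0.10, 2.0 at d = 0.20. Zero at d = 0.15 / 0.651 = 23%.
- r = 0.5: 7.5, 1.0 and −5.5 points. Zero at d = 0.075 / 0.651 = 11.5%.

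**4. Status-on-Day-14 reading.** Let s be the share of recovering oral patients still on PN at Day 14. With q = 0.15 and no such failures in the NJ arm, the gap is 0.15 × s: 0, 7.5 or 15 points for s = 0, 0.5 or 1.

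**5. Intake that differs by arm.** Write qO and qN for the two arms. Against a common Day 5 PN rule, the artificial part of the difference is qN × (1 − r). Against an endpoint that ignores PN, it is qO − qN × r. With qO = 20%, qN = 5% and r = 0, these are 5 and 20 points.

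**The case against.** **The endpoint is tied to Day 14.** Both the objective and the definition's heading say so. A reader taking them as status on that day would score the patient in step 1 as a success in both arms, provided PN had stopped. This stands as a limit: that reading shrinks the problem and can remove it. But the text does not choose it and gives no PN stopping rule, so PN begun at Day 5 may still be running.

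**NJ patients should rarely be low at Day 5.** The schedule reaches full nutrition by 72 hours. Even the second-day rate gives 50 × 24 = 1,200 ml. The 60% mark is 0.60 × 30 = 18 kcal/kg/day. At an assumed 1.0 kcal/ml, 1,200 / 18 covers patients up to about 67 kg (50 kg at 0.75 kcal/ml, 100 kg at 1.5). Where severe intolerance causes the shortfall, a separate component may already apply. This also stands in part: the equal-intake figures should not be read as a forecast, and fewer NJ patients are exposed to the different scoring. But the schedule is a target rather than achieved intake, and the endpoint itself allows for shortfalls in both arms. Step 5 shows that a small qN does not remove the effect if the yardstick is Day 14 intake.

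**Something may lie outside the visible text.** The flow figure is not shown and could hold an NJ rescue step. An unseen SAP could fix the counting window, though it could not set who receives PN at the bedside.

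**Infection outcomes.** A reader might infer that unequal PN use also biases the infection comparison, because the background says "several randomized trials have linked total parenteral nutrition (TPN) with an increased risk of infections and other complications". That statement concerns total PN. The oral arm receives PN as a supplement to diet, and the documents do not link that to infection. I do not rely on it.

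**Conclusion.** The point holds conditionally. The one-sided PN rule and the two-sided PN component are both in the current text. Equal oral or enteral intake can be scored differently by arm if any single component suffices and either PN counts at any time up to Day 14 or PN begun at Day 5 is still running then. The likely direction is against oral feeding, because PN is compulsory there and optional in the NJ arm. The direction is not certain (step 3).

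The size cannot be derived from the documents. The tables show only how the gap moves with assumed inputs, and no single figure from them should be quoted as the bias. A reader might infer that the two failure rates cannot be compared at all, or that PN is barred in the NJ arm. Neither follows: the status reading can remove the problem, and the NJ section is silent rather than prohibitive. The false-significance figures likewise rest wholly on the assumed q.

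The point merits an amendment because it touches the primary comparison and is cheap to correct. It does not undermine a feasibility pilot as such.

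**What to change.** Use the same PN trigger in both arms: supplement when oral or enteral intake is below 60% of 30 kcal/kg/day at Day 5. State that any one component makes a failure. Then choose one scoring rule:

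- **Option A, keep PN in the endpoint.** Score the PN component in both arms as meeting the trigger at Day 5, whatever PN was actually given. The 75% component stays at Day 14.
- **Option B, a pure Day 14 status endpoint.** Drop PN use as a component. Score failure as oral or enteral calories below 75% of target at Day 14, with PN calories excluded, plus severe GI intolerance.

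Either option removes the different scoring of equal intake by construction.

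The cost is a wording amendment and a separate row for PN calories on the form. Day 5 and Day 14 intake are already collected in both arms, and no extra patients or procedures are needed. The price is that some NJ patients with early feed interruptions will receive PN or count as failures. Under Option A, patients who recover by Day 14 still count as failures, but equally in both arms.
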